- 1) **Personalized Genomic Testing for Skin Cancer – Maximizing Utility and Reach – 05/16/17**
- (v. 10)
- 2) **IRB Review History N/A**
- 3) **Objectives**

This study will have two phases, with an added usability test after Phase I and before Phase 2. Phase 1: Cognitive Interviews in Spanish.

Phase 2: Personalized Genomic Testing for Skin Cancer (PGT-SC).

The overarching goal of this study is to learn more about how to maximize the availability, comprehension and appropriate uptake of personalized genomics among different populations in New Mexico. The proposed study has been funded as an R01 by NCI for three years.

Aim I: To examine the personal utility (that is, how does personal genomic testing help the individual) of Personal Genomic Testing for Skin Cancer (PGT-SC) in terms of short-term (three months after testing) sun protection, skin screening (i.e., behaviors), communication, melanoma threat and control beliefs (i.e., putative mediators of behavior change). Guided by Protection Motivation Theory (Robberson and Rogers, 1998), **we hypothesize that behaviors and putative mediators will be higher in those who test, compared to those who decline testing or wait-list controls.**

Aim Ia. An important challenge of personal genomics involves the potential for those who receive “negative” genetic feedback to increase risky behaviors (McBride et al., 2010). To examine this potential unintended consequence of testing, we will conduct a subgroup analysis among those who receive average risk PGT-SC findings, examining sun protection at three months as the outcome. Predictors will include baseline skin cancer threat and control beliefs, skin cancer risk factors, and demographics. These findings will be used in future studies to develop messages for groups that receive average risk feedback, which accounts for large segments of those tested for moderate risk susceptibility factors across many diseases.

Aim II: To examine differential reach of PGT-SC across Hispanics and Non-Hispanics, and potential explanations for any differential reach. Reach is defined as the extent to which genomic testing is spread throughout the population. Reach will be measured in individuals as the consideration of the pros and cons of testing and registration of test decision. Additional assessments of reach include baseline survey completion and decision to pursue PGT-SC testing. **We hypothesize that those who are self-identified Hispanic will show reduced reach, but that differences in health literacy, health system distrust, and Hispanic sociocultural factors (Marin G, et al., 1987) including cancer fatalism (Espinosa de Los Monteros and Gallo, 2011), family health orientation (Pasick et al., 2009), and skin cancer misperceptions (Torres et al., 2014; Roman et al., 2013) will explain differences in reach between Hispanics and Non-Hispanics, and provide guidance for future PGT-SC modifications for Hispanics.**

Aim III: Among those who undergo testing, to examine (two weeks after PGT-SC test result receipt) test comprehension, recall, satisfaction, and cancer-related distress, and

whether these outcomes differ by ethnicity (Hispanic versus Non-Hispanic) or health literacy, distrust, sociocultural, or demographic factors. **We hypothesize, based on prior work delivering this intervention in primary care, we will have high test comprehension, accurate feedback interpretation, and low test distress in those who get tested (Kaphingst et al., 2012).**

4) **Background**

Personalized genomics currently has extremely limited reach (Hindorff et al., 2009; Green and Guyer, 2011). *First*, most gene discovery has not engaged diverse research cohorts (James et al., 2008). *Second*, the few translational research efforts that address “real world” genomic challenges and opportunities have engaged those with higher socioeconomic status and health literacy (Khoury et al., 2011). *Third*, ethnic and racial minorities are less likely to participate in basic genomics research, and are also less likely to utilize available genomic technologies, even when they are offered (Pagan et al., 2009; Bloss et al., 2010; Suther et al., 2009). Ideally, we should all have fair access to the knowledge gained from sequencing the human genome, but if these trends continue, we will know little about how to maximize availability, comprehension, and appropriate uptake of personalized genomics across large subpopulations that stand to benefit from it.

To begin to address this, The Multiplex Study led by the National Human Genome Research Institute (NHGRI) used population-based recruitment strategies in Detroit, Michigan to evaluate an Internet-provided offer of genomic testing for common diseases, including melanoma, the most serious form of skin cancer. Study findings indicate that this approach is *feasible* – resulting in high test comprehension, accurate feedback interpretation, and low test distress in those who sought testing (Kaphing et al., 2012). Yet this study did not include Hispanics nor assess behavioral outcomes.

Personalized genomic testing for skin cancer (PGT-SC) is an ideal context to extend Multiplex to a new population, and new outcomes. Skin cancers are preventable, curable, very common in the general population (Lazovich et al., 2012), and disproportionately increasing in Hispanics (Rouhani et al., 2010). The NHGRI Multiplex Study offered testing for melanoma risk via the melanocortin 1 receptor gene (*MC1R*) (Wade et al., 2010) because *MC1R* is common in the general population (50% \geq 1 high risk variant) (Demenais et al., 2010), interacts with sun exposure (Udayakumar and Tsao, 2009), and confers risk (2-3 fold (Raimondi et al., 2008); consistent with most moderate risk variants), *even in those with darker skin types*. *MC1R* feedback is a promising vehicle to raise risk awareness and protective behavior in the general population, including Hispanics who are largely unaware of their melanoma risks (Friedman et al., 2994; Hu et al., 2009; Piptone et al., 2002; Robinson et al., 2011). We will conduct a randomized controlled trial examining internet presentation of the risks and benefits of PGT-SC (shown to be feasible in Multiplex) versus wait-list controls who are not offered testing, comparing personal utility and reach in a general population, English or Spanish-speaking cohort in Albuquerque, New Mexico, where there is year-round sun exposure.

Prior investigator collaborations. This transdisciplinary effort will bring together the combined expertise of investigators – many of whom have productive, longstanding collaborations already - to integrate up-to-date research findings from their respective disciplines, a necessary step given that the rapid unfolding of new cancer genomic, communication, and behavioral science findings is the expected reality of these fields (Wade et al., 2009). We employ a Multiple PI Plan. [name], Principal Investigator is an expert in risk communication and behavior change who has worked with [name], Principal Investigator, a genetic epidemiologist and a leader in the field of the genetic factors in melanoma for over 10 years. Drs. [name] and [name] conducted studies examining family communication and health behavior change (screening, sun protection) in melanoma families, and found a high rate of discussion about melanoma risk in melanoma families, ([name] et al., 2005) that different patterns of family communication after melanoma diagnosis influence adoption of prevention strategies, ([name] et al., 2005; [name] et al., 2008) inconsistent adoption of such strategies in survivors, (Majumdar et

al., 2009) and that behavioral outcomes associated with hypothetical melanoma genetic testing differ based on positive versus negative risk feedback. ([name] et al., 2012).

University of New Mexico (UNM) primary care patients are receptive to skin cancer genomic communication; UNM Hispanics report higher skin cancer misconceptions. Drs. [name] and [name] conducted a pilot study in the UNM 1209 Clinic to examine 1) patients' receptivity to behavioral research studies in skin cancer and genetics, 2) to document levels of sunscreen and protective clothing use, shade-seeking, and health provider skin cancer screening examinations, 3) to examine prior health information-seeking and family cancer discussions, and 4) prevalence of accurate skin cancer beliefs. Most (71%) participants were female and they ranged in age from 19-81 years (n=50), with racial/ethnic subgroups consistent with the Albuquerque population (46% were Hispanic, 35% were Non-Hispanic White, 6% Native American, 3% African American, and 10% other). Nine percent had not completed high school, and 55% had household incomes less than \$30k/year. About one third (30%) reported a family skin cancer history and 7% a personal skin cancer history. About two-thirds (66%) reported interest in behavioral skin cancer research, and while few (17%) had heard of genetic testing marketed directly to consumers, two thirds (76%) said they would be interested in learning more about genetic testing for skin cancer. Sun protection and skin cancer screening levels were consistent with recent national data; 29% reported that they consistently used sunscreen, 62% wore a shirt with sleeves, 34% a hat, and 47% sought shade often or always while outside on a sunny day. Even fewer (26%) had ever received a health provider skin examination. Non-Hispanic Whites reported more consistent use of sunscreen, and were more likely to have received a prior health provider skin examination than Hispanics and other racial/ethnic groups (all p values <0.01). Two-thirds (62%) reported that they were moderately or highly likely to develop skin cancer. Predominant reasons for heightened risk included current or past sun exposure, fair skin, and family history or genetic factors. Spontaneous health information-seeking was common, with 72% reporting that they had ever sought information on medical topics, predominantly via the internet. Over half (62%) had sought cancer information. About half (55%) had talked about cancer risk, and 37% about skin cancer risk, in their family. Those with higher perceived skin cancer risk talked more about it with their family ($r=0.34$, $p=0.001$) and were more interested in skin cancer behavioral research participation ($r=0.26$, $p=0.01$). We assess skin cancer misconceptions as an explanation for reduced PGT-SC reach in Aim II of the current study, because Hispanics reported more skin cancer misconceptions than Non-Hispanic Whites in our UNM pilot study. Over half of Hispanics endorsed confusion about which skin cancer recommendations to follow, and significant proportions of Hispanics agreed with the statement "it seems likely almost everything causes skin cancer" (24%); and "people with skin cancer would have pain or other symptoms prior to diagnosis" (24%; Torres et al., 2014). Also in our prior work with nationally representative samples, we found that Non-Hispanic Whites had higher awareness of accurate skin cancer causes, prevention strategies, and symptoms than Hispanics. Hispanics reported higher levels of information overload and misconceptions. ([name] et al., 2009).

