C) Baseline Assessment. All participants approached will be asked to complete a three minute Eligibility Screening and a Screening Survey to determine their interest in and eligibility for study participation, as well as basic demographics. If they are eligible and interested in study participation, the PA will fully explain the study and the participant will provide written informed consent (Consent - Number 2 and UNMHSC_HIPAA_Authorization), receiving a copy of the signed consent form. The PA will guide them to complete the Baseline Questionnaire in the clinic in a semi-private space with dedicated study computer (tablet or laptop computer).

Based on prior research, we anticipate that 30% of those approached will participate and complete the Baseline Questionnaire. Sample size estimates indicate that a total number of participants of 885 is necessary to evaluate our outcomes.

After completion of the Baseline Questionnaire facilitated by the PA, participants will receive a \$15 Target Gift card for their time and effort. They will sign a Sombra Gift Card Form and receive a Sombra Appointment Card. They will then be randomized to Group 1 - wait-list controls or to Group 2 to consider PGT-SC through a secure website (randomized and balanced across Hispanic and Non-Hispanic ethnicity, n=120 in control arm, n=530 in PGT-SC arm). "Hispanic" ethnicity will be recorded by self-report. Patients will choose Spanish or English study materials.

D) PGT-SC Invitation. (Group 2 – n=530)

Participants randomized to the PGT-SC study arm will view materials on the SOMBRA Website via Internet from a home, work, library or community-based organization computer, or alternatively through a paper version of the modules if they prefer. Internet reach in Albuquerque is >80% and WiFi is available throughout the city. All participants will be asked to consider the four educational modules regarding PGT-SC. The PGT-SC modules are:

- 1) What genetic testing can and cannot tell you,
- 2) Skin cancer and genes,
- 3) Your rights if you take part in genetic research, and
- 4) Your decision to be tested or not.

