After each module, participants will be asked to answer a series of questions regarding knowledge and satisfaction with the content of each module, and after section 4 they will be asked to register a decision as to whether they wish to have a skin cancer genetic test, or not. Participants will only be able to register a test decision if they have already read and completed the questions on the first three educational modules. Knowledge and satisfaction questions are part of each module. Those who complete these steps will receive an additional \$5 target Gift card incentive for each module for a maximum a total of \$15 in Target Gift card incentives. There is no incentive associated with the 4th module on the decision to conduct genetic testing or not.

Registration of a test decision (yes; no) is our primary assessment of "reach" in this study. We expect a minimum of 30% of participants who complete the Baseline Survey to register a genetic test decision, and that this will reach 50% in some subgroups, including those with higher literacy. Additional assessments of "reach" include completion of the baseline survey and decision to pursue PGT-SC testing (yes; no).

Those who register a decision to proceed with testing will receive a DNA buccal cell test kit with instructions (Donor Mailing Form and Specimen Collection Form), which will allow them to provide a saliva sample for genetic testing, pre-paid postage envelope, and instructions in English and Spanish for buccal cell collection. Based on The Multiplex Study, we anticipate that up to 50% of participants who consider PGT-SC will return a saliva sample for genetic testing. The Molecular Epidemiology Laboratory at UNM HSC will conduct testing; participants will receive PGT-SC results by mail (or by email, if they prefer) within one month.

We will employ state-of-the-art methods of risk communication used with high comprehension in the Multiplex Study, guided by Co-Investigator [name], who originally developed Multiplex Study risk communication materials. These materials combine verbal and pictorial displays of risk information and denominator information. We will also provide written information to clarify risk level given that individuals tend to rely on the gist of the information provided (See SOMBRA Result A for average risk individuals and SOMBRA Result B for higher risk individuals)

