All subjects who participate in PGT-SC genetic testing will receive a telephone call two weeks after results are mailed, to assess PGT-SC result comprehension and potential distress (see Two Week Risk Feedback Comprehension Assessment) and to answer any questions they may have. All those who

complete this Assessment will receive a \$5 Target Gift card as thanks for their effort. Based on prior literature documenting low levels of distress in those undergoing genetic testing for high-risk mutations, and among those found to carry *CDKN2A* mutations, we anticipate low levels of distress regarding PGT-SC feedback. Anyone who reports high distress will be referred to Clinic Director and Co-Investigator [name], who addresses distress issues regularly in the UNM clinic. If they wish, a genetic counselor will be available.

E) Three-month follow-up.

All participants who completed Baseline Assessments (whether tested or not) will be contacted for assessment by telephone three months after PGT-SC testing (Three Month Follow Up Questionnaire). Participants who complete this three-month follow up assessment will receive a \$15 Target Gift card for their valued study participation.

F) Group 1 genetic testing option.

Those 120 participants randomized to the control group will receive an offer for PGT-SC directly after the three-month follow-up assessments. They will be offered testing, and of those who pursue testing, will receive results by mail or by email, sent by the PA who enrolled them, and a two-week follow-up telephone call to assess result comprehension and potential distress.

G) Summary.

We anticipate that patients will be enrolled over an approximately 12 month period, complete assessments and receive feedback within 20 months. Thus individuals are estimated to be in the study for 3 months and the enrollment and assessment period overall will last as long as 20 months total. Primary analyses will be completed in the 6 months following the 24 months period of participation; the entire study will take 3 years.

9) Study Endpoints.

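### Aim I's comparison of testers with wait-list controls cannot isolate the effect of genomic testing, and its tester-versus-decliner comparison holds education constant only under a definition the plan does not give

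*Combined protocol and SAP*

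**What the plan says.** Section 3 gives the purpose of Aim I: "To examine the personal utility (that is, how does personal genomic testing help the individual) of Personal Genomic Testing for Skin Cancer". Its hypothesis is that "behaviors and putative mediators will be higher in those who test, compared to those who decline testing or wait-list controls". Section 9 carries personal utility forward as a primary endpoint from the three-month questionnaire.

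Section 8D describes what the PGT-SC arm (Group 2, n=530) receives. "All participants will be asked to consider the four educational modules regarding PGT-SC", and there is a gate before any decision: "Participants will only be able to register a test decision if they have already read and completed the questions on the first three educational modules". The registered decision can be yes or no. Those who test also get a telephone call two weeks after results are mailed, which assesses comprehension and distress and answers their questions.

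Section 8F describes the control arm: "Those 120 participants randomized to the control group will receive an offer for PGT-SC directly after the three-month follow-up assessments". Section 11 lists payments to this arm for the baseline and three-month surveys only.

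The Background (section 4) describes the randomised comparison in different terms from Aim I: internet presentation of the risks and benefits of PGT-SC, against controls who are not offered testing. Section 13 names intention-to-treat but does not say how the two Aim I contrasts will be modelled, or which of them supports a conclusion about testing.

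**The concern.** Aim I draws its conclusion about testing, but testers and wait-list controls differ in at least three ways by the time the outcome is measured. Testers have completed three modules with questions, they have chosen to be tested, and they have received an MC1R result followed by a call. A difference between these groups cannot be assigned to any one of the three.

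The Aim I outcomes (sun protection, screening, communication, threat and control beliefs) are ones that education about skin cancer and genes could plausibly move. If it did, the trial could report that genomic testing has personal utility when the result itself had added nothing. A health system reading that conclusion would pay for genotyping when the web modules might have been enough.

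The second comparator, people who decline testing, could hold the education constant. The plan does not define who counts as a decliner, so it is not clear that it does.

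**Working it through.** **Exposure of each group before the three-month assessment (sections 8D, 8F and 11)**

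| Group | Modules 1-3 | MC1R result and call | How the group is formed |
|---|---|---|---|
| Testers | all completed | yes | own choice within Group 2 |
| Registered a no | all completed | no | own choice within Group 2 |
| Never registered | none, some or all | no | own choice within Group 2 |
| Full PGT-SC arm | mixed | mixed | randomised |
| Wait-list controls | none planned | no | randomised |

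Testers versus controls differ in every column. Testers versus registered decliners differ in the result and call, and in self-selection. Only the full arm versus controls is randomised, and it estimates the effect of the package.

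**Group sizes**

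Inputs: 530 in the PGT-SC arm and 120 controls (sections 6 and 8C); at least 30% registering a decision, reaching 50% in some subgroups (section 8D); the expectation that "up to 50% of participants who consider PGT-SC will return a saliva sample" (section 8D); up to 20% lost at three months (section 13). I apply 30-50% to the whole arm and read those who consider PGT-SC as those who register.

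- Registered: 530 × 0.30 = 159 to 530 × 0.50 = 265.
- Never registered: 530 − 159 = 371 to 530 − 265 = 265.
- Testers, at half of those registered: about 80 to 133. The remaining 80 to 133 are registered decliners.
- Followed up: testers about 64 to 106 (× 0.8); controls 120 × 0.8 = 96.

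If decliners included everyone who did not test, the 265-371 people who never registered would outnumber the 80-133 with known full module exposure, and the contrast would again differ in education.

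**Illustration of the effect on the tester-versus-control contrast**

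The plan gives no module effect, SD, alpha or power for this contrast, so there is no figure of its own to reproduce. Assumed: two-sided alpha 0.05, no test effect, no self-selection, and a module effect e of 0.1 to 0.3 SD. The expected difference is then exactly e. Its standard error in SD units is √(1/n₁ + 1/n₂):

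- 64 testers, 96 controls: √(1/64 + 1/96) = 0.161
- 106 testers, 96 controls: √(1/106 + 1/96) = 0.141

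The probability of a significant result favouring testers is Φ(e/SE − 1.96). For e = 0.2 this is Φ(1.239 − 1.96) = 0.24 and Φ(1.420 − 1.96) = 0.29.

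| Assumed module effect | 64 testers | 106 testers |
|---|---|---|
| 0.1 SD | 0.09 | 0.11 |
| 0.2 SD | 0.24 | 0.29 |
| 0.3 SD | 0.46 | 0.57 |

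With no module effect the two-sided rate would be 0.05. The opposite tail adds at most 0.005 to any cell.

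**Sensitivity to uptake**

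Section 6 expects 30-50% of those offered to accept testing. Read as testers, that is 159-265 of 530. At the upper end (212 followed up) the three probabilities become 0.13, 0.37 and 0.68. The bias stays equal to e; only the chance of calling it significant changes.

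A module effect that is equal in testers and registered decliners cancels in the contrast between them.

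**The case against.** The strongest reply is that Aim I names two comparators. Anyone who registers a no has completed the same three modules, so that contrast can separate the result from the education. This stands. A reader might infer that Aim I as a whole credits testing with whatever the modules do; the documents do not support that, because the fault lies in the wait-list contrast. The decliner contrast is only a partial remedy: it is self-selected, and it loses its advantage if people who never registered are counted in it.

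Three further points limit the finding.

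- Both arms meet the NCI skin cancer pamphlet at recruitment (section 7), so controls lack the modules, not all skin cancer information. Of the three modules, one covers skin cancer and genes, one genetic testing and one research rights. Their content is not shown, so a module effect is plausible but not established, and its size is assumed here.
- A reader might go further and divide the arm difference by the proportion tested, which would inflate the apparent test effect because untested module completers also carry any education effect. No section plans such a scaling. The ratio of module completers to testers is also unsettled, since sections 6 and 8 use their uptake percentages with different denominators. No figure of that kind should be held against the plan.
- The documents often use PGT-SC for the whole arm, and section 4 already describes the randomised comparison as an offer against no offer. Part of the fault is therefore loose wording. But the hypothesis names those who test, and that is an analysis group, not only a label.

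**Conclusion.** The point holds in this form: testers versus wait-list controls cannot show what testing adds, because modules, self-selection and result arrive together. Testers versus decliners can hold the modules constant if decliners are defined as registered noes, but that contrast remains non-randomised. The randomised comparison of full arms is sound and answers a different question, the effect of the invitation package.

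The exposure pattern follows from the documents alone. The size rests on assumptions: any module effect passes in full into the tester-versus-control difference, and at 0.1 to 0.3 SD it would give a significant result with probability from about 0.09 to 0.57, on about 64-106 testers and 96 controls with no self-selection. Self-selection could add to or offset this, and the documents give no basis for its size. It would not be right to conclude that the trial is invalid or that Aim I cannot be addressed at all. The stated conclusion needs to match the contrast that supports it.

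**What to change.** 1. In Aim I and section 9, state the randomised conclusion as the intention-to-treat effect of the PGT-SC invitation package (modules, optional test and follow-up call) versus no invitation, comparing full arms as randomised.
2. Define decliners as participants who completed modules 1-3 and registered a no. Report those who never registered as a separate group.
3. Base any claim about the test itself on testers versus these decliners, adjusted for baseline values of the outcome and for baseline characteristics related to choosing the test, and label it observational.
4. If testers versus wait-list controls is kept, present it as descriptive and say that it includes the effect of the modules and of self-selection.

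No new arm, participant or measurement is needed, since module completion and the registered decision are already to be recorded. The cost is a narrower headline: the randomised evidence will concern the offer of testing with its education, and evidence on the MC1R result will be weaker and rest on roughly 64-106 people per group after loss, on the figures above.
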